SD	Standard Deviation
SDTM	Study Data Tabulation Model
SMQ	Standardized MedDRA Query
SOC	System Organ Class
VRR	Vaccine Response Rate
YOA	Years of Age

Version history

SAP Version	Approval Date	Protocol Version (Date) on which SAP is Based	Change	Rationale
SAP	25 Jan 2022	8 June 2021	Not Applicable	Original version
SAP Amendment 1	29 Apr 2022	8 June 2021	
 • New blinded early safety analyses are added into Section 4.6 Other analyses • Changes to Introduction section and Section 4.8 	SAP amended to accommodate Drug Controller General of India (DCGI) requirement for early safety data
SAP Amendment 2	16 Sep 2022	25 May 2022	
 • Analysis to be performed for Blinded early safety report has been moved from section 4.6 to section 4.7 as it is now included in the protocol amendment 1 and two new tables have been added to the report • Section 6.2.2.1 a point added for date imputation • Changes to section 6.2.2.3.1 to count denominator correctly for fever solicited adverse event • Changes to section 6.2.3.1 for calculation of age 	Based on protocol amendment 1

SAP Version	Approval Date	Protocol Version (Date) on which SAP is Based	Change	Rationale
SAP Amendment 3	11 Nov 2022	25 May 2022	
 Changes to section 4.7.1 – item 5 to remove related and grade 3 related from solicited systemic events output 	As per protocol, all solicited administration site and systemic events occurring within 7 days of study intervention administration will be considered causally related to the study intervention

1. INTRODUCTION

The purpose of this SAP is to describe the planned analyses to be included in the CSR and in the analysis planned for the Blinded Early Safety Report for Study ZOSTER-081 (214461).

1.1. Objectives and Endpoints

Objectives	Estimands/Endpoints
Primary	
To determine the vaccine response rate (VRR) for anti-gE humoral immune response at 1-month post-dose 2 (Month 3) of administration of HZ/su*.	Percentage of participants showing a vaccine response for anti-gE antibody concentrations at 1-month post-dose 2 (Month 3).
Secondary	
To evaluate the anti-gE humoral response at 1-month post-dose 2 (Month 3) in recipients of HZ/su compared to Placebo**.	Anti-gE antibody concentration expressed as group geometric mean concentration (GMC) ratio at 1-month post-dose 2 (Month 3).
To evaluate safety and reactogenicity following administration of HZ/su or placebo from first dose up to 30 days post last dose.	
Solicited AEs: Number and percentage of participants reporting each solicited administration site AE (injection site redness, pain, swelling and pruritus) and solicited systemic AEs (fever, myalgia, fatigue, gastrointestinal [GI] symptoms, headache and shivering) within 7 days (Day 1 to Day 7) after each dose and overall.
 
Unsolicited AEs: Number and percentage of participants reporting unsolicited AEs within 30 days (Day 1 to Day 30) after any dose.
 
SAEs: Number and percentage of participants reporting SAEs from Dose 1 (Day 1) up to 30 days post last dose.
 
pIMDs: Number and percentage of participants reporting pIMDs from Dose 1 (Day 1) up to 30 days post last dose.

To evaluate safety following administration of HZ/su or placebo during the entire study period.	
SAE- Number and percentage of participants reporting SAEs from Dose 1 (Day 1) up to study end (phone contact Month 8).
 
pIMDs- The number and percentage of participants reporting pIMDs from Dose 1 (Day 1) up to study end (phone contact Month 8).

To characterise anti-gE humoral immunogenicity response prior to the first study intervention administration (Day 1) and at 1-month post-second study intervention administration (Month 3) in both groups.	Anti-gE antibody geometric mean concentrations (GMC) and seropositivity rate at pre-study intervention administration (Day 1) and 1-month post-dose 2 (Month 3). Mean geometric increase (MGI) at 1-month post-dose 2 (Month 3) compared to pre-study intervention administration (Day 1).

*The success criteria for the primary objective and VRR definition are presented in Sections 4.2.2 and 4.2.1 respectively

**The success criteria for the secondary objective are presented in Section 4.3.3

[figure not shown]
Primary Estimand

The primary clinical question of interest is to show that the immunogenicity for anti-gE antibody is comparable in the Indian population with respect to the vaccine response rate (VRR) 1 month post Dose 2 of *Shingrix* vaccination in eligible participants who complied with the study intervention (refer to section 3 for the definition of the per protocol set used for the primary analysis and to section 4.2.2 for the statistical method).

1.2. Study Design

The overview of the study design is presented in [Figure 1](#) below.

Figure 1 Study design overview

*BS=Blood Sampling; Int=study intervention, N=number of participants planned to be randomised;

‡ Each participant will be followed up for 6 months post last dose/Month 8.

- **Type of study:** Self-contained.
- **Experimental design:** Phase 3, randomised, observer-blind, placebo-controlled, multi-centric, single country study with 2 parallel groups (see [Figure 1](#)).
- **Duration of the study:** Approximately 8 months for each participant.
- **Control:** Placebo-controlled
- **Blinding:** Observer-blind
- **Study intervention schedule:** 0 and 2 months (Day 1 and Month 2)
- **Biological samples:** Blood samples will be collected at Day 1 and Month 3 (1-month post-dose 2).

- **Follow-up contact:** Phone contact at Month 8 (6 months post last study intervention administration).
- **Primary completion date (PCD):** Month 3 (1-month post-dose 2).
- **Data collection:** Standardised electronic Case Report Form (eCRF). Solicited AEs and unsolicited AEs will be collected using a Participant Diary card (paper diary card).
- **Study groups:** Refer to [Table 1](#) for an overview of the study groups.

Table 1 Study groups, intervention and blinding

Study Groups	Number of participants	Age	Study intervention	Blinding
				Visit 1→Phone contact (Observer-blind)
HZ/su	144	≥ 50 years	VZV gE	X
			AS01 _B	
Placebo	144	≥ 50 years	Lyophilised sucrose	X
			Saline (NaCl) solution for reconstitution	

- **Study intervention assignment:** The study will enrol approximately 288 participants who will be randomised 1:1 to the HZ/su or Placebo group of equal size to receive 2 doses of study interventions administered intramuscularly 2 months apart. The randomisation algorithm will use a minimisation procedure accounting for age (50- 69 YOA, ≥ 70 YOA). Minimisation factors will have equal weight in the minimisation algorithm.
- **End of Study (EoS):** End of Study (EoS) is achieved after Last subject* last visit (LSLV=Phone contact at Month 8) or Date of the last testing/reading released of the Human Biological Samples or imaging data, related to primary and secondary endpoints (whichever is later).

*subject=participant.

2. STATISTICAL HYPOTHESES

The study has one primary and one secondary immunogenicity confirmatory objective which will be assessed in a hierarchical manner. The null hypothesis related to the primary objective under consideration is that the VRR for anti-gE antibody concentration 1 month after the second HZ/su dose is $<60\%$.

The primary objective will be met if the lower limit (LL) of the 95% Confidence Interval (CI) of the VRR for anti-gE antibody concentration 1 month after the second HZ/su dose is $\geq 60\%$.

The null hypothesis related to the secondary confirmatory objective under consideration is that the adjusted GMC ratio between the HZ/su and the Placebo group for anti-gE antibody concentration 1 month after the second study intervention dose is <3 .

The secondary confirmatory objective will be met if the LL of the 95% CI of the adjusted GMC ratio between the HZ/su and the Placebo group for anti-gE antibody concentration 1 month after the second study intervention dose is ≥ 3 .

All the safety analyses and humoral immunogenicity response under the secondary objective are descriptive.

2.1. Multiplicity Adjustment

The hypotheses are tested hierarchically, so no multiplicity adjustment is required.

3. ANALYSIS SETS

Analysis Set	Definition/Criteria
Enrolled Set	Eligible participants who have signed an informed consent and were randomised or undergone an invasive procedure.
Exposed Set (ES)	All participants who received at least 1 dose of the study intervention. Analysis per group using the enrolled set is based on the administered intervention.
Per Protocol Set (PPS)	All eligible participants who received all doses as per protocol, had immunogenicity results pre- and post-dose 2, complied with allowed dosing/blood draw intervals (Table 2), without intercurrent conditions that may interfere with immunogenicity and without prohibited concomitant medication/vaccination. The analysis will be done according to the study intervention that participants received at dose 1.

3.1. Intervals between study visits

The intervals allowed for the inclusion of the PPS is the ‘allowed interval per protocol’ as defined in [Table 2](#) below:

Table 2 Intervals between study visits

Interval	Planned visit interval	Allowed interval range	Allowed interval during special circumstances
Visit 1→Visit 2	60 days/2 Months	49 days-83 days [#]	49 days–180 days
Visit 2→Visit 3	30 days/1 Month	28 days-48 days [#]	28 days–60 days
Visit 2→Phone contact	180 days/6 Months	160-210 days	160–210 days

[#]Participants may not be eligible for inclusion in the PPS, if study visits occur outside the allowed interval.

3.2. Criteria for eliminating data from Analysis Sets

Elimination codes are used to identify participants to be eliminated from analysis. Details are provided below for each analysis set.

3.2.1. Elimination from Enrolled Set

Code 800 (fraudulent data), 900 (invalid ICF) and 1010 (treatment number not allocated) will be used for identifying participants eliminated from Enrolled Set.

3.2.2. Elimination from Exposed Set (ES)

Code 1030 (Study treatment not administered at all), 800 (fraudulent data), code 900 (invalid informed consent) and code 1010 (treatment number not allocated) will be used for identifying participants eliminated from ES.

3.2.3. Elimination from Per-protocol analysis Set (PPS)

3.2.3.1. Excluded participants

A participant will be excluded from the PPS analysis under the following conditions. Please note that impact of COVID-19 on the per protocol set will be determined on a case by case basis.

Code	Condition under which the code is used	Visit (timepoints) where the code is applicable
800	Fraudulent data	All
900	Invalid ICF	Visit 1
1010	Treatment number not allocated	Visit 1
1030	Study intervention not administered at all	Visit 1
1040*	Administration of concomitant vaccine(s) forbidden in the protocol Any concomitant vaccination not foreseen by the study protocol administered in the period starting 30 days before the first dose of the study vaccine and ending at Visit 3 (Day -30 to Month 3)	Visit 1 to Visit 3
1050	Randomisation failure	All
1060	Randomisation code was broken	Visit 1 to Visit 3
1070**	Study intervention not according to protocol: - 
Participants got vaccinated with the correct study intervention but containing a lower volumeAdministration not according to protocol for reason specified by investigator other than route, side and site.Site and route of study intervention is wrong or unknown	Visit 1, Visit 2

Code	Condition under which the code is used	Visit (timepoints) where the code is applicable
	
 Wrong replacement or study intervention administered (not compatible with the vaccine regimen associated to the treatment number) 	
1080	Temperature deviated study intervention administered	Visit 1, Visit 2
1090	Expired study intervention administered	Visit 1, Visit 2
2010	Protocol violation (inclusion/exclusion criteria)	Visit 1
2040*	Administration of any medication forbidden by the protocol (refer to Section 5.2.1 and 5.2.2 of the protocol) in the period from the first dose of study intervention and ending at Visit 3 (Day 1 to Month 3)	Visit 1 to Visit 3
2050*	Underlying medical condition forbidden by the protocol Any intercurrent medical condition (IMC) (refer to section 9.3.1 of the protocol) which can affect the immune response to the study intervention during the study up to Visit 3 (Day 1 to Month 3)	Visit 1 to Visit 3
2060*	Concomitant infection related to the vaccine which may influence immune response	Visit 1 to Visit 3
2080	Participant did not comply with study intervention schedule DOSE 1 – DOSE 2 = 49-83 days	Visit 2
2090	Participant did not comply with blood sample schedule DOSE2-blood sample (BS)2 = 28-48 days	Visit 3
2100	Serological results not available post-vaccination Check for humoral result for PPS	Visit 3
2120	Obvious incoherence or abnormality or error in data Check for humoral result for PPS	Visit 3
2500	Participant who didn't receive two doses	Visit 2

*Attribution of these elimination codes to participants need CRDL review of individual listing

**Attribution of these elimination codes will be evaluated on case-by-case basis and requires CRDL confirmation

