4.2. Primary Endpoints Analyses

The primary immunogenicity analysis will be performed on the PPS and if more than 5% participants are eliminated from the PPS then a complementary analysis will be performed on ES.

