4.2.1. Definition of endpoints

The VRR is defined as the percentage of participants who has at least:

- a 4-fold increase in the post last vaccination anti-gE antibody concentration as compared to the pre-vaccination anti-gE antibody concentration for participants who are seropositive at baseline.
OR
- a 4-fold increase in the post last vaccination anti-gE antibody concentration as compared to the anti-gE antibody cut-off value (97 mIU/ml) for seropositivity for participants who are seronegative at baseline.

Two-sided 95% CIs for VRR will be computed by Clopper-Pearson method [[Clopper, 1934](#)].

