4.3.1.2. Definition of endpoints

The geometric mean concentration (GMC) calculations are performed by taking the anti-log of the mean of the log base 10 concentration transformations. For descriptive statistics only, antibody concentrations below the cut-off of the assay will be imputed with a value equal to half the cut-off for the purpose of GMC calculation.

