5. SAMPLE SIZE DETERMINATION

Approximately 288 (144 participants per study group) eligible participants will be randomised to achieve 200 (100 participants per study group) evaluable participants for the evaluation of the primary objective assuming that approximately 30% of the enrolled participants will not be evaluable. Participants who withdraw from the study will not be replaced.

Considering a 95% VRR in the HZ/su group, the study has at least 99% power to meet the primary objective under the hypothesis given below:-

- Null hypothesis: The VRR for anti-gE ELISA at 1 month after second HZ/su dose in participants from India is less than 60%.
- Alternative hypothesis: The VRR for anti-gE ELISA at 1 month after second HZ/su dose in participants from India is at least 60%.

Power to show the LL of the 95% CI for VRR at one month after second HZ/su dose.

Endpoint	NI criteria	N1:N2 (evaluable)	Reference**	Power*
Vaccine response rate – anti-gE ELISA	LL of 95% CI for VRR $\geq 60\%$	100:100	95%	$\geq 99\%$

*Power computed using PASS 2019 software, Non-Inferiority Test for one proportion, 1-sided alpha=2.5%;

**References used for the sample size calculation: ZOSTER-006 study.

Considering the adjusted GMC ratio of 44.31 between HZ/su and Placebo group and SD of 0.30 and 0.46 for HZ/su and Placebo group, respectively, the study has at least 99% power to meet the secondary confirmatory objective under below hypothesis.

- Null hypothesis: The adjusted GMC ratio for anti-gE ELISA at 1 month after second study intervention dose in participants from India is less than 3.
- Alternative hypothesis: The adjusted GMC ratio for anti-gE ELISA at 1 month after second study intervention dose in participants from India is greater than or equal to 3.

Power to show the LL of the 95% CI for adjusted GMC ratio at one month after second dose.

Endpoint	Criteria for evaluation	N1:N2 (evaluable)	Reference**	Power*
Adjusted GMC ratio	LL of 95% CI for adjusted GMC ratio ≥ 3	100:100	Adjusted GMC ratio – 44.31 SD for HZ/su group – 0.30 SD for Placebo group – 0.46	$\geq 99\%$

*Power computed using PASS 2019 software, Two-Sample T-Tests for Superiority by a Margin Allowing Unequal Variance,

1-sided alpha=2.5%;

**References used for the sample size calculation: ZOSTER-006 study.

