6.1.3. Protocol Deviations

The number of participants enrolled into the study as well as the number of participants excluded from the per protocol set (PPS) analyses will be tabulated for the total population.

The number of participants enrolled into the study as well as the number of participants excluded from the ES will be tabulated for the total population. This will be based on all enrolled participants.

Important protocol deviations will be summarized. Protocol deviations which result in exclusion from an analysis set will also be summarized. Data will be reviewed prior to unblinding and freezing the database to ensure all deviations leading to analysis population exclusions are captured and categorised in the protocol deviations ADaM dataset.

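### Could elimination code 2120 remove valid but unexpected month-3 anti-gE results from the primary Per Protocol Set?

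*SAP*

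**What the plan says.** SAP 3.2.3.1 lists the codes that take a participant out of the PPS. Code 2120, applicable at Visit 3, reads "Obvious incoherence or abnormality or error in data", with the note "Check for humoral result for PPS". Results that are missing have their own code (2100), so 2120 concerns results that exist. The footnotes to the table require CRDL review or confirmation for codes 1040, 1070, 2040, 2050 and 2060. Code 2120 carries no such mark.

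The same Visit 3 result feeds the primary endpoint. For participants seropositive at baseline, SAP 4.2.1 defines response as at least "a 4-fold increase in the post last vaccination anti-gE antibody concentration as compared to the pre-vaccination anti-gE antibody concentration". For seronegative participants the comparison is with the assay cut-off. It also feeds the secondary confirmatory GMC ratio (SAP 4.3.1.3).

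The primary analysis is on the PPS, but "if more than 5% participants are eliminated from the PPS then a complementary analysis will be performed on ES" (SAP 4.2). Removal from the ES is limited by SAP 3.2.2 to "Code 1030 (Study treatment not administered at all), 800 (fraudulent data), code 900 (invalid informed consent") and code 1010 (no treatment number). Code 2120 is not among them. On timing, SAP 6.1.3 states: "Data will be reviewed prior to unblinding and freezing the database to ensure all deviations leading to analysis population exclusions are captured".

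**The concern.** An exclusion rule that operates on the outcome variable deserves suspicion. In code 2120 an abnormality is an alternative to an error, so on a literal reading no error is needed. Neither document says what counts as abnormal or requires a laboratory, sample or data-entry cause. The PPS definition in Protocol 9.3 asks only that pre- and post-dose-2 results exist, and Protocol 9.3.1 gives no ground based on an odd result.

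Review before unblinding protects less than usual here. The planning assumptions are "Considering the adjusted GMC ratio of 44.31 between HZ/su and Placebo group and SD of 0.30 and 0.46 for HZ/su and Placebo group, respectively", so a month-3 titre largely reveals the arm to anyone who sees it. The documents do not say whether those assigning the codes see titres. If HZ/su non-responders were dropped, the VRR would be biased upward. If low HZ/su or high placebo values were dropped, the GMC ratio would be. Both confirmatory objectives are decided on the PPS.

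**Working it through.** **Inputs.** 100 evaluable per group, planned VRR 95%, criterion of a lower 95% limit of at least 60%, GMC ratio 44.31 with SDs 0.30 and 0.46, 288 randomised, about 30% not evaluable (SAP 5); Clopper-Pearson limits (SAP 4.2.1). The SDs are taken as log10, because SAP 4.3.1.2 obtains GMCs by "taking the anti-log of the mean of the log base 10 concentration transformations". The documents give no expected count for code 2120, so the removals below are illustrations.

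**The plan's own figures.** With n = 100, the smallest passing count is 70 (lower limit 60.02%; 69 gives 58.97%). The exact one-sided error at a true VRR of 60% is 0.0248, and power at 95% is essentially 1, so the stated power of at least 99% reproduces. For the GMC ratio, (log10 44.31 − log10 3) / √(0.30²/100 + 0.46²/100) = 1.169 / 0.0549 = 21.3, again power of about 1.

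**Can a titre reveal the arm?** With an equal-error threshold, correct identification is Φ(log10 44.31 / (0.30 + 0.46)) = Φ(1.6465 / 0.76) = Φ(2.17) = 98.5%. It is about 93% with SDs 50% larger, 91% at a ratio of 10, and 81% with both. This part of the concern is right.

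**Effect on the VRR estimate if HZ/su non-responders were removed.**

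| Responders / n | VRR | Lower limit |
|---|---|---|
| 95/100 | 95.0% | 88.7% |
| 95/99 | 96.0% | 90.0% |
| 95/95 | 100% | 96.2% |

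**Effect on the decision.** It can change only with 69 or fewer responders in 100. At 69, one removal is not enough: 69/100 gives 59.0%, 69/99 gives 59.6% and 69/98 gives 60.3%. The probability of 69 or fewer is about 1e-16 at a true VRR of 95%, 4e-5 at 85%, 0.6% at 80% and 10% at 75%.

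**Effect on the GMC ratio.** In simulated trials of 100 per arm (log10-normal, no covariates), dropping the two lowest HZ/su and two highest placebo values moves the ratio from 44.3 to about 48. Dropping two at both ends of both arms leaves it at 44.3. The planned unadjusted 95% interval is 10^(1.6465 ± 1.96 × 0.0549), or about 34.6 to 56.8. Even the wholly one-sided case lies inside that interval and far above 3.

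**Will the ES analysis be run?** SAP 4.2 does not say whether the 5% is pooled or per group. Pooled, 5% of 288 is 14.4, so 15 exclusions trigger it. The chance of that is 91% if 7% are excluded, 99.9% at 10%, and about 1 at the planned 30%. Per group, 5% of 144 is 7.2, while 30% of 144 is about 43, so the planned loss is again far above the trigger.

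**The case for a change.** The best case for a change is that the wording permits what a primary analysis set should not permit, and that the code most exposed to the outcome lacks the review mark given to five others. The ES analysis is only complementary and does not decide success. The VRR estimate is itself the primary objective, so bias in it matters even when the pass is safe. A cure would cost one table row.

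Some of this stands. The term is undefined, the mark is absent, and blinding is weak for anyone who sees titres. What does not stand is the step from a loose word to a biased result. For that, the people assigning the code must see titres, infer the arm, call a valid result obviously abnormal, and do so mostly in the favourable direction. Nothing in the documents points to any of the last three. An unusual value can as easily be a very high HZ/su titre or a very low placebo one, and symmetric removal leaves the GMC ratio unchanged.

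The stricter rule that suggests itself, barring any reference to titre size or fold-rise, has its own cost. An incoherent pre/post pair is often the first sign of a swapped or mislabelled sample. If no laboratory record then confirmed the swap, a plainly wrong pair would stay in the primary set.

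**Conclusion.** No change is needed. Read in its place, code 2120 is a data-integrity check: the defect must be obvious and must lie in the data, and the SAP treats failure to reach a 4-fold rise as an endpoint outcome. Analysts would fill the undefined term that way.

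The plan also makes departures from that reading visible. The laboratory is blinded (Protocol 6.3.4), exclusions are reviewed before unblinding and summarised (SAP 6.1.3), and a table shows the passage from ES to PPS (SAP 6.1.1). An analysis that puts any code 2120 cases back is close to certain at the planned 30% loss.

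The possible effect is about 1 point of VRR for each HZ/su non-responder removed, and a GMC ratio of about 48 in place of 44.3 if two removals per arm all went the favourable way. At the planned VRR the success decision is not realistically affected. This rests on the planning values of SAP 5. If the true VRR were near 75%, about 10% of trials would have a count at which selective removals could matter, but that would still require the code to be used against its natural meaning. A line tying exclusion to a documented laboratory, sample or data error would do no harm if the SAP were reopened, but sound results do not depend on it.
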